13.2 Definitions

Evaluable: All study-eligible patients who receive at least one infusion of nivolumab will be considered *evaluable for safety and toxicity*. To be *evaluable for efficacy*, patients must be study eligible, receive at least one cycle (6 weeks) of immunotherapy and complete initial disease assessment at ≥ 6 weeks after starting therapy.

Exclusions: Any patient who is enrolled on study, but does not receive any component of study treatment, will be excluded from all efficacy analyses. Any patient who initiates treatment and is later found to be ineligible for study (e.g., protocol violation) will be withdrawn from study but will be followed for disease progression, toxicity and survival. The experience of such patients will be characterized separately from that of evaluable patients. Reasons for exclusion of enrolled patients from the analysis set for efficacy, or for safety, will be characterized.

Overall response rate (ORR): Overall response rate is the proportion of patients whose best overall response per modified iRANO criteria or standard RANO criteria is complete (CR) or partial (PR) after at least 6 weeks from start of therapy. iRANO additionally requires best overall response of CR or PR to be sustained, that is, confirmed by a second assessment at \geq 4 weeks later. Patients who clinically progress before the initial radiographic assessment after 1 cycle (6 weeks) will be considered nonresponders.

Progression-free survival (PFS): PFS will be measured from the start date of treatment until

documented evidence of disease progression, clinical progression or death from any cause, after at least 8 weeks from start of therapy. Radiographic progression should be confirmed by a second assessment at \geq 4 weeks later. For patients who remain alive without progression, follow up time will be censored at the date of last assessment.

Overall survival (OS): Survival will be measured from the start date of treatment to the date of death from any cause or last contact (censored observations).

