11.1 Definitions

Evaluable for Objective Response Only those patients with measurable disease present at baseline will be enrolled on study.

Only patients who received at least one cycle (6 weeks) of therapy and response assessment with brain MRI or CT at least 6 weeks from the first dose will be considered evaluable for overall survival or disease progression. Patients who discontinue therapy for reasons other than progression prior to response assessment will not be evaluable for survival and will be replaced.

Only patients with measurable disease present at baseline, completing at least one cycle (6 weeks) of therapy, and disease re-evaluated radiographically will be considered evaluable for partial or complete response.

Any patient who initiates treatment and is later found to be ineligible for study (e.g., protocol violation) will be withdrawn from study but will be followed for disease progression, toxicity and survival. The experience of such patients will be characterized separately from that of evaluable patients. Reasons for exclusion of enrolled patients from the analysis set for efficacy, or for safety, will be characterized.

Evaluable Non-Target Disease Response

Patients with lesions present at baseline that are evaluable but do not meet the definitions of measurable disease, have received at least one cycle (6 weeks) of therapy, and have had their disease re-evaluated will be considered evaluable for non-target disease. The response assessment is based on the presence, absence, or unequivocal progression.

All patients who have received at least one dose infusion of nivolumab and/or initiate TTFields therapy are evaluable for safety and toxicity.

Disease Parameters

For the purposes of this study, patients will be evaluated for response approximately every 6 weeks of therapy starting from the first dose for the initial 24 months, thereafter approximately every 8 weeks. In addition to baseline scans, confirmatory scans will be obtained at \geq 4 weeks following initial documentation of objective response or disease progression.

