13. STATISTICAL CONSIDERATIONS

13.1 Study Design and Sample Size

We propose an open label, two parallel arm, two-stage, phase II trial to determine the efficacy, in terms of objective response rate (ORR), of combination therapy with tumor treating fields (TTFields) therapy, nivolumab with or without ipilimumab in adult patients with bevacizumabnaïve, recurrent glioblastoma. Best objective response rate (ORR) is defined as the proportion of evaluable patients who achieve complete (CR) or partial response (PR) according to modified immunotherapy iRANO criteria. Secondary objectives include safety, ORR by standard RANO criteria, overall survival (OS), progression-free survival (PFS), clinical benefit (defined as ORR plus stable disease >12 weeks), compliance rates of TTFields therapy at or above goal of 75%, and exploratory correlations between response or survival and compliance rates, serum and/or tumor tissue biomarkers. Primary analyses are performed for each arm, but secondarily assessed for the entire cohort as well.

The EF-11 study showed a response rate of 14% among patients with recurrent glioblastomas treated with TTFields alone compared to physician's choice medical therapy (Stupp et al, Eur J Cancer 2012). Thus, the null H0 is set at 14% and H1 (target ORR) set at 35% for each arm. Power is set at 85% with a 1-sided alpha of 0.05.

If no response is seen after 15 eligible patients are accrued in either arm, that arm will close for futility. Based on a MiniMax design, if >2 responses are seen on the first 15 patients in either arm, then 15 more patients will be accrued in the arm. If \geq 7 responses are seen among the 30 patients in either arm, this regimen deserves further investigation. Sample size will be 30 maximum per cohort/arm for a total of 30 to 60 subjects enrolled on study.

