13.4 Statistical Analyses

Baseline characteristics will be summarized using descriptive statistics: count, percentage, range, median, mean, and standard deviation as appropriate. Data include demographics (age, sex, race/ethnicity), performance status, laboratory parameters and prior therapy.

Treatment duration will be summarized by the number of immunotherapy cycles (6 weeks each). Frequency and reason for dose modifications and discontinuation of any therapy will be detailed.

We will report the objective response rate with corresponding two-side 90% confidence interval (CI) using the exact binomial method (Armitage et al, 2002). We will also report the objective response rate, the median and range for time to response, and duration of CR or PR. Time to progression will be summarized by the median and range for patients whose best response is SD as well as for all patients who develop progressive disease.

The Kaplan-Meier method will be used to estimate progression-free and overall survival. Point estimates for the proportion of progression-free and surviving patients will be given for selected times, specifically 6 and 12 months, along with corresponding 95% confidence intervals using the log-log transformed method and Greenwood's variance. To the extent possible with 30-60 study patients, we will investigate the relationship between tissue and serum biomarkers and overall response using logistic regression. Similarly, biomarker associations with progression free and overall survival will be explored using the log rank test and Cox regression.

Safety will be assessed by tabulating toxicities according to type, grade, duration, and attribution to study treatment in accordance with *NCI Common Terminology Criteria for Adverse Events* (CTCAE version 4.0). We will also report the distribution of worst grade toxicity in study patients.

TTFields compliance data is collect during monthly in-home visits by Novocure representative in order to assess NovoTTF200A (OptuneTM) function and address patient concerns. The compliance rates are an average (mean \pm stdev) over the 28-31 days of the month and provided in graphical and numerical form. Appendix D shows sample compliance reports with weighted average (mean \pm stdev) per month. These data are provided as part of standard of care and included in the patient medical record. The weighted average will be compared to ORR, OS and PFS using the appropriate logistic or Cox regression models.

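### Sections 13.2 and 11.1 define different safety sets, and following 13.2 leaves treated patients later found ineligible out of the main toxicity rates

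*Combined protocol and SAP*

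**What the plan says.** Section 13.2 (Definitions) sets the safety population with two conditions, eligibility and one nivolumab infusion: "All study-eligible patients who receive at least one infusion of nivolumab will be considered" evaluable for safety and toxicity.

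Section 11.1 (Definitions) uses exposure alone: "All patients who have received at least one dose infusion of nivolumab and/or initiate TTFields therapy are evaluable for safety and toxicity".

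Section 13.2 then deals with patients who start treatment and are later found ineligible. They are "withdrawn from study but will be followed for disease progression, toxicity and survival", and "The experience of such patients will be characterized separately from that of evaluable patients". It adds: "Reasons for exclusion of enrolled patients from the analysis set for efficacy, or for safety, will be characterized". Section 11.1 carries the same three provisions.

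Section 13.4 (Statistical Analyses) plans tables of toxicity by type, grade, duration and attribution, and adds: "We will also report the distribution of worst grade toxicity in study patients". It names no denominator and does not refer to either definition.

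**The concern.** Safety is a secondary objective (sections 1.3 and 13.1), and the toxicity tables are its main product. Two analysts working from the two sections could report different rates from the same data.

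The eligibility condition is the part that matters. A safety set normally rests on exposure, because the question is what happened to the people who were treated. Under 13.2, membership also depends on a finding that can come after treatment has begun. The criteria are pre-treatment conditions, but in these patients the failure is discovered late. The trial is open-label and the investigator confirms eligibility (section 12.2.2), so a patient's toxicity may already be known when the finding is made. Some criteria plausibly bear on tolerance: organ and marrow function and unresolved earlier adverse events (section 3.1), recent surgery and autoimmune disease (section 3.2). With at most 30 patients per arm, one to three patients can visibly move a rate.

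**Working it through.** **Step 1. The rules side by side.**

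| Question | Section 11.1 | Section 13.2 | Section 13.4 |
|---|---|---|---|
| Must the patient be eligible? | No | Yes | Not stated |
| Exposure that qualifies | Nivolumab and/or TTFields | At least one nivolumab infusion | Not stated |
| Treated, later found ineligible | Toxicity followed, described apart | Toxicity followed, described apart | Not stated |
| Exclusions from the safety set foreseen? | Yes | Yes | Not stated |

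The first row is a direct conflict. The last two rows show that 11.1 is not consistent with itself: it admits every exposed patient, yet describes the ineligible ones apart from the evaluable ones and foresees safety exclusions. The second row is a smaller difference. It affects only a patient who starts TTFields without any nivolumab, which should be rare because sections 1.1 and 5.1 plan infusions to start promptly while the device awaits insurance approval.

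**Step 2. How far a rate can move.** The plan states no figure here to reproduce, so the inputs are partly assumed:

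- N = 30 treated in one arm, the maximum per arm in section 13.1.
- x = 6 patients with a given toxicity (assumed).
- k = 1 to 3 treated patients later found ineligible (assumed; the documents give no number).
- j = how many of those k had the toxicity, from 0 to k.

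All-treated rate = x/N = 6/30 = 20.0%. Rate under 13.2 = (x − j)/(N − k).

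| k | No ineligible patient had the event (j = 0) | All of them had it (j = k) |
|---|---|---|
| 1 | 6/29 = 20.7% | 5/29 = 17.2% |
| 2 | 6/28 = 21.4% | 4/28 = 14.3% |
| 3 | 6/27 = 22.2% | 3/27 = 11.1% |

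The 13.2 rate falls below the all-treated rate only when j/k exceeds x/N, that is, when the ineligible patients have more toxicity than the treated group as a whole. Otherwise it stays the same or rises.

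**Step 3. How often an event would fall outside the main rate.** Suppose each ineligible patient independently carries a true 20% risk, the same as everyone else. The chance that at least one affected patient is left out is 1 − (1 − 0.20)^k: 20% for k = 1, and 1 − 0.512 = 49% for k = 3. Equal risk means no systematic bias, but an exposed patient's event would still often be missing from the main table.

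**The case against.** The strongest reply is that this is mostly a matter of presentation. Toxicity in these patients is still followed, their experience is described separately and the reasons for exclusion are given. Section 7 records all adverse events, and section 7.1 collects serious events from consent onward, related or not. A reader with both reports could rebuild the all-treated rate, provided the separate report is detailed enough. Safety is descriptive, with no test. The interim rule in section 13.5 concerns futility on response, and no numerical toxicity boundary uses this denominator. The study team and the DSMB see toxicities as they arise. All of this stands, and it keeps the point small.

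Three stronger readings are tempting, and the documents do not support them:

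- **That these patients' toxicity goes unreported.** It does not. Both sections require follow-up and separate description. What is lost is their place in the main rates.
- **That the plan understates toxicity.** No passage links late-discovered ineligibility to higher toxicity. Several criteria have no evident link to it, such as IDH mutation status, infratentorial disease or measurable disease. The effect can go either way, and the lower figures in the table require every ineligible patient to have had the event.
- **That 11.1 is sound and only 13.2 is wrong.** Section 11.1 has the same provisions for separate description and safety exclusions, so both need editing.

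What the reply does not answer is the conflict itself. The sections give different denominators, neither is marked as prevailing, and the reference in 13.4 to study patients does not choose between them.

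**Conclusion.** The point holds as a minor inconsistency with a clear remedy. Sections 11.1 and 13.2 define different safety sets, 13.4 does not settle which applies, and 11.1 is in tension with its own all-patients rule. If 13.2 is followed, exposed patients leave the main toxicity rates on a finding made after exposure, though they are reported elsewhere.

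The actual size is unknown. In the illustration, one ineligible patient moves a 20.0% rate by about three percentage points at most. Three can lower it by about nine points or raise it by about two. These figures rest on the assumed 6 events in 30 and the assumed 1 to 3 ineligible patients. A downward bias is conditional on more toxicity among the ineligible. No response analysis, stopping rule or sample-size calculation is affected.

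**What to change.** Use one safety set in 11.1, 13.2 and 13.4: all patients who received any component of study treatment (nivolumab, ipilimumab or TTFields), regardless of later eligibility findings. In 13.4, name that set as the denominator for every toxicity table. Flag ineligible treated patients in those tables, or list them in addition. In both 11.1 and 13.2, limit the sentence on separate description to efficacy, and remove ineligibility as a ground for exclusion from the safety set.

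The cost is a wording amendment to three sections. Toxicity follow-up of these patients is already required, so no new data are needed, and the primary endpoint and sample size are unaffected.

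### PFS, OS and ORR definitions disagree on how events in the first 6 to 8 weeks are counted; if early events are dropped, PFS and OS rates read high

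*Combined protocol and SAP*

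**What the plan says.** **PFS.** Section 13.2 starts the clock on the first day of treatment and defines the event as "documented evidence of disease progression, clinical progression or death from any cause, after at least 8 weeks from start of therapy". Its censoring rule covers only patients who are alive and progression-free. Section 11.3.3 treats clinical deterioration, or failure to return because of death or decline, as progressive disease and sets no minimum time.

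**OS and the progression set.** Section 11.1 opens its rule on who is evaluable for OS or progression with "Only patients who received at least one cycle (6 weeks) of therapy and response assessment with brain MRI or CT at least 6 weeks", counted from first dosing. The next sentence is narrower: "Patients who discontinue therapy for reasons other than progression prior to response assessment will not be evaluable for survival and will be replaced". The OS definition in 13.2 runs from treatment start to death or last contact and has no such window.

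**ORR.** Section 11.1 says that patients with measurable disease "completing at least one cycle (6 weeks) of therapy, and disease re-evaluated radiographically will be considered evaluable for" partial or complete response. Section 13.2 likewise says that efficacy-evaluable patients must "receive at least one cycle (6 weeks) of immunotherapy and complete initial disease assessment". Section 13.1 refers to evaluable patients without defining them. Yet the ORR definition in 13.2 adds: "Patients who clinically progress before the initial radiographic assessment after 1 cycle (6 weeks) will be considered nonresponders". The Exclusions paragraph there says: "Any patient who is enrolled on study, but does not receive any component of study treatment, will be excluded from all efficacy analyses".

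Section 13.4 reports Kaplan-Meier PFS and OS at 6 and 12 months.

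**The concern.** The PFS and OS clocks start on day 0, but one clause qualifies events by week 8 and another admits patients only once they have reached a scan at week 6 or later. Following either literally removes people because they failed early, while the rest keep their event-free time from day 0. That raises every later Kaplan-Meier estimate.

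For the primary endpoint, a patient who deteriorates clinically in week 4 is outside the evaluable set under one sentence and a nonresponder inside it under another. In an open-label trial, that choice should not be left until outcomes are known.

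**Working it through.** **1. Which events are exposed.** Progression first seen on the week-6 scan can still count, because confirmation at least 4 weeks later falls at about week 10. The exposed PFS events are deaths and clinical progressions before week 8. For OS they are deaths before a week-6 scan.

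**2. What could happen to an exposed event.**
- Counted on its date: no bias.
- Dated at week 8: the 6- and 12-month rates are unchanged.
- Patient removed: the rates rise.
- Censored: 13.2 gives no basis for this, since it censors only patients alive without progression. It is not used below.

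**3. The plan's own figure.** The plan gives no design figure for PFS or OS. For ORR, Section 13.5 states a 65% chance of early stopping under the null. With p = 0.14 and stopping at 2 or fewer responses in 15:

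0.86^15 + 15(0.14)(0.86^14) + 105(0.14^2)(0.86^13) = 0.104 + 0.254 + 0.290 = 0.648. This agrees.

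With success at 8 or more of 30, the exact one-sided error is 0.046 and power at 35% is 0.852. Section 13.1 prints 7 or more, which is a separate matter; 8 is used here because it fits the stated 0.05 and 85%.

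**4. Size of the PFS and OS effect if events are removed.**

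Inputs:
- 6-month PFS of 21% (TTFields arm of EF-11, Section 2.2.2).
- Median PFS of 3.5 and 4.6 months (glioblastoma patients in the retrospective cohort, Section 2.6.2).
- Median OS after TTFields of 6.5 and 8.3 months (same cohort).
- Cut L: 8 weeks = 56/30.4375 = 1.840 months for PFS; 6 weeks = 42/30.4375 = 1.380 months for OS.

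Assumptions, not in the documents: exponential shape, and the share f of early events that is removed.

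Formula: apparent S(T) = S(T) / (1 - f(1 - S(L))).

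Worked case: a 21% 6-month PFS implies a median of 6 ln 2 / (-ln 0.21) = 2.665 months, so 1 - S(1.840) = 0.380, or 11.4 of 30 patients. At f = 0.25, 0.21/(1 - 0.095) = 0.232. At f = 0.50, 0.21/(1 - 0.190) = 0.259. At f = 1, 0.21/0.620 = 0.339.

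| Rate at 6 months | Early events | True | f = 0.25 | f = 0.50 | f = 1 (extreme) |
|---|---|---|---|---|---|
| PFS, from 21% | 38.0% | 21.0% | 23.2% | 25.9% | 33.9% |
| PFS, median 3.5 | 30.5% | 30.5% | 33.0% | 36.0% | 43.9% |
| PFS, median 4.6 | 24.2% | 40.5% | 43.1% | 46.1% | 53.4% |
| OS, median 6.5 | 13.7% | 52.7% | 54.6% | 56.6% | 61.1% |
| OS, median 8.3 | 10.9% | 60.6% | 62.3% | 64.1% | 68.0% |

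At f = 0.10, 6-month OS reads 53.5% and 61.3%, a shift under 1 point. At 12 months with f = 0.25 to 0.50, OS of 27.8% reads 28.8-29.9% and OS of 36.7% reads 37.7-38.8%.

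**5. Power if early progressors are counted.** If 35% describes only scanned patients and a fraction q progresses before the scan, the response probability is 0.35(1 - q). At q = 0.05 (0.3325) power for 8 or more of 30 is 0.804; at q = 0.10 (0.315) it is 0.746, against 0.852 at q = 0.

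**The case against.** The documents can be read benignly. The nonresponder sentence in 13.2 may be a specific exception to a general evaluability rule. The replacement sentence in 11.1, with the death-or-deterioration criterion in 11.3.3, suggests that early tumour deaths and progressions stay in, and the OS definition has no window. The 8-week phrase may be a displaced version of the 8-week persistence requirement in 11.3.3. Entry requires KPS of at least 60, so early deaths may be rarer than an exponential curve implies. The plan also promises disclosure: "Reasons for exclusion of enrolled patients from the analysis set for efficacy, or for safety, will be characterized".

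Much of this stands. It makes the extreme column unlikely and means that upward bias is a possibility, not a certainty. It does not settle the text: the opening sentence of the 11.1 rule still excludes the patients whom the next sentence implies are kept, and no section says what happens to a death at week 5. Listing reasons for exclusion discloses the loss but fixes no denominator.

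A reader might go further in two ways that the documents do not support. One is to treat the Exclusions paragraph as defining a third, all-treated ORR denominator. It names never-treated patients but does not say that they are the sole exclusion, and it goes on to mention other exclusions. The other is to conclude that the ORR type I error is inflated. That requires the 14% null to describe all treated patients, which the plan does not state; if it describes evaluable patients, there is no inflation.

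**Conclusion.** The textual conflict is firm: Sections 11.1, 11.3.3 and 13.2 give incompatible or missing rules for early events in PFS, OS and ORR. If early deaths or progressions are dropped, the bias in PFS and OS is upward. Its size is illustrative only. With 25-50% of early events removed, 6-month PFS rises by about 2 to 6 points and 6-month OS by about 2 to 4 points, under exponential curves and a share that has no source in the documents. For patients who leave alive through toxicity or withdrawal, an upward direction is likely but not certain.

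PFS and OS are secondary, have no comparator and drive no go/no-go decision. ORR does drive it, and there the defect is an unsettled denominator, not a demonstrated error rate. This should be fixed before analysis, but it does not invalidate the design.

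**What to change.** 1. Delete the 8-week clause from the PFS definition in 13.2, and count progression, clinical progression and death from treatment start. Reconcile the 8-week persistence wording in 11.3.3 with the 4-week confirmation in 11.3.3 and 13.2.
2. Analyse PFS and OS in all eligible patients who receive any study treatment, including those replaced, and amend 11.1 to match.
3. Amend the evaluability rules in 11.1 and 13.2 so that patients who progress, deteriorate or die before the first scan are in the ORR denominator as nonresponders.
4. Report ORR in all eligible treated patients, with unassessed patients as nonresponders, beside the evaluable-set ORR. Replacement of patients who leave without progressing, and the two-stage count, stay as they are.
5. State in 13.1 which population the 14% and 35% describe.

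The cost is wording and one added analysis set. Sections 5.4 and 5.10 already provide survival follow-up until death, loss to follow-up or withdrawal of consent. Reported PFS, OS and all-treated ORR may be somewhat less favourable. If the 35% target describes only scanned patients, counting 5% or 10% early progressors brings the power loss shown above, which is a further reason for item 5.
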